Baseline-Monitoring Phase (Phase 1): The subject will track her/his headaches daily for 28 days through an online survey tool (REDCap, licensed through Columbia University), to establish a baseline headache frequency. Each day, the subject will receive a text message/e-mail reminder to complete the daily headache log. The message will contain a link to log into the survey tool. During this phase, subjects will answer questions including presence or absence of headache symptoms, severity of headache symptoms, duration of symptoms, impact on daily activities, and use of rescue medication. Any headache lasting more than 24 hours will be counted as a second headache day. After 28 days of monitoring, the study coordinator will assess the subject's data to make sure the subject meets criteria for minimum headache days, and has been consistently performing the daily log. If the number of headache days is insufficient, the subject's participation will be completed. If the subject logs at least 6 headache days in the month, she/he will continue in the study. If the participant has been assigned to the Episodic arm of the study, but has >14 headache days in the screening month, or if the participant has been assigned to the Chronic arm of the study, but has <15 headache days in the screening month, she/he will NOT be reassigned, but will remain in the assigned group for analysis. The subject will then be treated with Brilinta/ticagrelor for a 28-35 day test period (Phase 2). The length of the test period will depend on the timing of the participant's follow-up visit after beginning treatment. The protocol window is 28+7 days.

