Treatment Phase (Phase 2): The subject will return for a follow-up visit to receive her/his medication within 1 week of completing the 28 day headache log. A loading dose of Brilinta/ticagrelor 180 mg will be administered in the office. Thereafter, for 28-35 days, a Brilinta/ticagrelor 90 mg tablet will be taken once in the morning and once in the evening, as close to 12 hours apart as possible. Each day, the subject will receive a text message reminder to login to the website, to record her/his headache activity. If she/he fails to login for two consecutive days, the study coordinator will place a follow-up phone call. PRU testing will be done a minimum of 7 days after the initiation of treatment, but before the medication is completed. A follow-up visit will be arranged between day 28 and day 35 days of monitoring to review efficacy, compliance, and side effects, to return unused medication, and to allow continued access to Brilinta/ticagrelor if indicated. A second Quality of Life survey will be completed.

Continued Access Phase (Phase 3): If the subject has a beneficial response to the Brilinta/ticagrelor (> 50% reduction in the average number of monthly headache days compared with the baseline), she/he will be offered continued access to the medication to complete an additional 2 months of therapy with on-going headache monitoring. A final office visit and Quality of Life Survey will be completed within 7 days of the 56th day of Phase 3 for return of unused medication, empty medication bottles and discussion about future therapeutic options. If the subject fails to have a beneficial response following the first month of treatment (Phase 2), the medication will be discontinued and participation in the study will be completed. If the subject elects to discontinue the Brilinta/ticagrelor, despite a beneficial response, participation in the study will be completed.

Outcomes Assessment/Statistical Analysis

Information from this study will be assessed to determine the feasibility of performing a larger randomized, blinded, placebo-controlled multi-center trial. We will assess not only our therapeutic drug response rate in order to estimate a required sample size for the future trial, but also our ability to recruit patients from local referring sources to estimate the time frame of such a trial. Subject compliance rate with use of daily online questionnaires will be determined. Drop-out rates, related to medication side effects will also be assessed.

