1. Statistical Considerations and Analysis Plan:

This is a prospective, open label single-armed trial designed to evaluate the safety and efficacy of Brilinta/ticagrelor (90 mg twice daily) used off-label, in a young healthy population, for the treatment refractory migraine headache. The primary endpoints are:

- Efficacy – Response to treatment defined as a $\geq 50\%$ reduction in chronic headache during a three month period of therapy, compared with baseline.
- Safety – Bleeding events and adverse medication reactions measured over the 3 month treatment period.

Only 40 subjects will be treated in this initial feasibility trial, 20 with episodic migraine, 20 with chronic migraine. We will assess the number of “Responders” in each study group. Responsiveness will be compared with the measured PRU while on therapy. The results of this trial will be descriptive only. It is not anticipated that the number of subjects enrolled will provide statistically analyzable results.

However, if treatment were to be seemingly beneficial, these data could form the foundation for the development of a pivotal randomized, blinded, prospective trial in a larger cohort as mentioned above.

The safety analysis set will include all subjects who receive at least one dose of study medication. This will be the primary analysis set for all safety endpoints which will include major bleeding complications, and adverse drug reactions. Bleeding outcomes, in this younger, healthier cohort will be compared with the previously published PLATO Trial²¹.

Any participant who completes her/his daily headache logs for at least two weeks, but not the full month of the study period, will be classified according to her/his current response status (LOCF), regardless of whether or not he/she completed the required therapy.

2. Analysis of Secondary Endpoints

The secondary endpoints, which will be reported, are as follows:

- Absolute reduction in headache days as a continuous response variable.
- Comparison of the use of rescue medications in the roll-in versus the treatment phase and “successful” interruption of MHA (< 2 hours to resolution) with rescue therapy.
- Non-major bleeding side effects of the medication

STUDY PROCEDURES:

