All potential subjects must have migraine headache documented by a Neurologist. All potential subjects must have a documented RLS by transcranial Doppler (see details above) prior to being a candidate for inclusion into the treatment group. All potential subjects will undergo baseline blood work testing and a urine pregnancy test if indicated. All subjects will take a migraine specific Quality of Life Survey (see below) at the start of the study and at visit #3 and at the conclusion of the continued access phase of the study (if applicable). All subjects will complete a daily headache log (see below), using the REDCap Survey Tool. Each subject will monitor headaches for the first month (28 days) while on her/his baseline medication, and will monitor headaches while also taking Brilinta/ticagrelor 90 mg twice daily for the second month (28-35 days). All subjects will undergo PRU blood testing a minimum of 7 days after the start of the Brilinta/ticagrelor therapy (but prior to its completion). A subject may be eligible for two additional months of Brilinta/ticagrelor therapy, with on-going headache monitoring, if she/he has a positive response to the medication.

STUDY DRUG:

Description:

Brilinta/ticagrelor, the first of a new class of oral anti-platelet agents (cyclopentyltriazolopyrimidines), is a non-competitive, P2Y12 receptor antagonist. Following a loading dose of 180 mg, the drug will be administered in its current FDA approved (2011) dosage of 90 mg twice daily.

[figure not shown]

Figure 1

Approved Uses:

Brilinta/ticagrelor is currently FDA approved as a prescription medicine for patients who:

- Have had a recent heart attack or severe chest pain that happened because their heart wasn't getting enough oxygen
- Have had a heart attack or chest pain and are being treated with medicines or procedures to open blocked arteries in the heart

Formulation/Dosage to be Used:

Brilinta tablets for oral administration contain 90 mg of ticagrelor and the following ingredients: mannitol, dibasiccalcium phosphate, sodium starch glycolate, hydroxypropyl

cellulose, magnesium stearate, hydroxypropyl methylcellulose, titanium dioxide, talc, polyethylene glycol 400, and ferric oxide yellow.

Dose Rationale and Risk/Benefits:

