There may be circumstances in which a participant may need to withdraw from the TRACTOR Migraine Trial. These may include either Serious or Important Adverse Events (as listed above), a change in health status (including need for urgent surgical or medical intervention, or unanticipated pregnancy), or non-compliance with the protocol. Non-compliance would be defined as recurrent failure to take the medication as directed, failure to keep protocol appointments, or repeated failure to enter headache log information despite reminders from the local study coordinator.

Any other serious adverse event, which might require discontinuation of the study drug, would require documentation of the issue by the local study team, with formal consultation with the Principal Investigator. An electronic Patient Withdrawal Form would need to be completed by the Principal Investigator. Any adverse event leading to subject withdrawal will require documented discussion by the Executive Committee, and a follow-up assessment by the local study team, to confirm the participant's return to baseline health status.

Once withdrawn from the TRACTOR Migraine Trial for medical reasons, all efficacy data collected to date will be maintained, but no further data will be collected. Any participant who completes the daily headache logs for at least two weeks while on treatment, but who does not complete the full four weeks of the study period, will be classified according to their current response status (LOCF), regardless of whether or not they completed the required therapy (see Outcomes Assessment).

Should a participant choose to withdraw consent for the TRACTOR Migraine Trial, at any time during the monitoring period, for reasons other than an adverse event, the participant must contact the principal investigator, who will complete an electronic Patient Withdrawal

Form. In such a circumstance, efficacy data already collected will no longer be eligible for review. However, safety data up to the point of participant withdrawal will be reviewable for the final data analysis.

MEDICAL MONITORING

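### The primary endpoint is stated over one month and over three, three-month logs cannot exist for month-1 non-responders, and neither the treatment days scored nor the scaling of partial logs is defined

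*Combined protocol and SAP*

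**What the plan says.** **Length of the endpoint window.** Working Study Definitions and Primary Study Endpoints both define a Responder by a reduction of at least 50% in monthly headache days over the month of therapy. The first speaks of an average number and the second only of a number. Statistical Considerations and Analysis Plan (item 1) instead gives the primary efficacy endpoint as a "reduction in chronic headache during a three month period of therapy, compared with baseline".

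**Who has data after month 1.** Under Continued Access Phase (Phase 3): "If the subject fails to have a beneficial response following the first month of treatment (Phase 2), the medication will be discontinued", and participation ends. Responders may also choose to stop at that point.

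**Days logged.** Phase 1 is a 28-day log "to establish a baseline headache frequency". For Phase 2: "The subject will then be treated with Brilinta/ticagrelor for a 28-35 day test period (Phase 2"). The same paragraph says "The length of the test period will depend on the timing of the" follow-up visit. Study Procedures describes logging on drug "twice daily for the second month (28-35 days").

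**Partial logs.** The analysis plan says that a subject with logs "for at least two weeks, but not the full month of the study period, will be classified according to her/his current response status (LOCF"). Withdrawal of Subjects repeats the rule for a subject with two weeks of logs on treatment "but who does not complete the full four weeks of the study period, will be classified according to their current response status (LOCF"). Both statements concern Responder classification only. No section gives a partial-log rule for the absolute reduction in headache days or for rescue use.

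**Use of the result.** Outcomes Assessment says the response rate will help to size the future trial. The analysis plan calls the results descriptive only.

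**The concern.** There are two separate defects.

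First, the documents give two windows for one primary endpoint, and one of them cannot be observed in every treated subject. An analyst who follows the analysis plan would have to invent a rule for everyone who leaves after month 1.

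Second, even on the one-month reading, the plan does not say which treatment days count or whether counts are divided by days logged. The same logs could therefore give different Responder labels. An unscaled count over more than 28 days works against the drug, and an unscaled count over fewer works in its favour. The label is the pilot's main output and an input to the next trial's sample size.

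**Working it through.** The plan states no power, alpha or expected response rate, so there is no figure of its own to reproduce.

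**Step 1: the two windows side by side.** The one-month window is planned for every treated subject. The three-month window needs Phase 3 logs, which Phase 3 itself rules out for month-1 non-responders. This follows from the text alone.

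**Step 2: what a raw count would require.** Let B be the 28-day baseline count, T the treatment days counted and d the true reduction in daily rate. The expected treatment count is T(1 - d)B/28. Setting this at or below B/2 gives d ≥ 1 - 14/T.

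- T = 14: 1 - 14/14 = 0%
- T = 28: 1 - 14/28 = 50%
- T = 35: 1 - 14/35 = 60%

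**Step 3: effect on the response rate.** From the documents: a 28-day baseline with at least 6 headache days, treatment of 28-35 days, and the split between episodic and chronic at 14/15 days. Assumed, because the documents give no figures: true rates uniform on 6-14 (episodic) or 15-26 (chronic) days per 28, independent days, and visits spread evenly over days 28-35. Then B ~ Bin(28, r/28) given B ≥ 6, and X ~ Bin(T, (1 - d)r/28). A subject is a Responder if X ≤ B/2 (raw) or X ≤ (B/2)(T/28) (rate).

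| True effect (assumed) | Episodic: days 1-28 → raw 28-35 | Chronic: days 1-28 → raw 28-35 |
|---|---|---|
| Every subject 50% | 59% → 48% | 54% → 38% |
| Mean 50%, between-subject SD 0.25 | 58% → 51% | 53% → 45% |
| Every subject 80% | 97% → 95% | 99.5% → 98.9% |
| 70% of subjects at 80-90%, 30% at 0-20% | moves 0 to 2 points | moves 0 to 2 points |

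The first row is an upper-end case, because it puts the whole cohort on the threshold. The last row spreads effects evenly within each range. At its least favourable corner (80% and 20%) the episodic shift is just under 3 points. Scaling to a rate but keeping all 28-35 days still gives 55% / 51% in the first row, so the choice of days matters a little even on a rate.

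**Step 4: partial logs.** An unchanged subject (d = 0) who stops at day 14 is labelled Responder in 58% / 54% (episodic / chronic) on raw counts, against 11-12% / 1% on a rate. Over a full 28 days the figure is 6% / 0.1%. The effect on the whole cohort depends on how many stop, which the documents do not give.

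**Step 5: absolute reduction.** Take an unchanged subject with 20 baseline days. Over 35 days the expected raw count is 20 × 35/28 = 25, an apparent 5-day increase. If the subject stops at day 14 it is 20 × 14/28 = 10, an apparent 10-day decrease.

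**Step 6: three-month reading.** This was simulated as three 28-day months, with month-1 non-responders counted as such and all others continuing. At a true 50% reduction it gives 40% against 59% (episodic) and 36% against 54% (chronic). Part of that gap is a different mismatch: continued access needs more than 50%, while the endpoint needs at least 50%. With at least 50% in both places the contrast is about 45% against 59% and 40% against 54%.

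**Step 7: scale of chance.** With 20 per cohort, the standard error near 50% is √(0.5 × 0.5/20) ≈ 0.11, or 11 points.

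**The case against.** The strongest reply is that the documents already point to a rate or to day 28. Study Design compares headache frequency with baseline and writes the period as 28 days plus 7. Working Study Definitions and Phase 3 refer to an average monthly number, and Withdrawal of Subjects to four weeks. Both appendices tie Visit 3 to day 28. On that reading days 29-35 are a visit window, and current status at day 14 means the reduction so far. This stands as evidence of intent. A reader might infer that the plan will compare raw counts over unequal windows, but the documents do not support that. What they lack is a rule: the primary endpoint omits the word average, and Study Procedures calls the whole 28-35 days the second month.

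It can also be said that the prior experience was split: 13 of 15 subjects had dramatic relief on clopidogrel, and 4 of 5 had complete elimination on prasugrel. In that case the 28-35 day shift is small. That is fair, although the protocol calls the benefit of this drug unknown.

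Finally, the pilot is descriptive, and the 7-8 point shift under varied effects is smaller than one standard error. That also stands, except that a shift caused by the scoring rule is systematic and avoidable.

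None of these replies touches the three-month contradiction.

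**Conclusion.** The plan contradicts itself on the length of the primary endpoint window, and the three-month version cannot be scored in all treated subjects. That conclusion needs no assumptions.

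The unstated treatment window and the undefined LOCF status are a gap in specification, not proof of a wrong analysis. If raw counts were used, the 28-35 day window would cost about 7-8 points of response rate when effects vary around 50% (about 1.5 subjects per 20). It would cost up to 10 (episodic) or 16-17 (chronic) points if every subject sat at 50%, and about 0-2 points under a split pattern. These sizes rest on the assumed rates, visit dates and effects above. The partial-log effect is large for each subject concerned but cannot be sized for the cohort without a dropout figure.

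No hypothesis test or error rate is affected. A reader might infer that the pilot's response rate will be wrong by the largest of these amounts. The documents support only that it could differ with the analyst's reading. It should be fixed before the logs are analysed, because the rate is carried into the next trial's sample size.

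**What to change.** - Reconcile the three-month wording in the analysis plan with the one-month definitions. Month 1 is the only window planned for every treated subject. Months 2-3 can be described separately among those who continue.
- Score the Responder endpoint, absolute headache-day reduction and rescue use on treatment days 1-28, per 28 logged days, with baseline in the same unit.
- For 14-27 logged days, replace the LOCF status with 28 × headache days / logged days.
- Report the number of subjects with fewer than 14 logged days as not evaluable.
- Optionally, as a sensitivity analysis only, count early stoppers as Non-responders.
- Reconcile the more-than-50% and at-least-50% thresholds noted in the working.

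The cost is one paragraph. Logs are daily, so no new data are needed. There are two downsides. Days 29-35 are not used for efficacy. Rates from 14-27 days are also noisier: at a true 80% reduction, a day-14 stopper is labelled Responder in 92% / 98% (episodic / chronic), against 97% / 99.5% over 28 days.

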Non-serious Adverse Event: any other adverse event that does not meet criteria for a serious adverse event.

Definitions of bleeding events are based on the PLATO Trial protocol²⁸, a previously published study comparing Brilinta/ticagrelor to clopidogrel.

- **Major Life-Threatening Bleeding** includes:
 - Any Fatal Bleed
 - Intracranial Hemorrhage
 - Intrapericardial bleed with cardiac tamponade
 - Bleeding resulting in hypovolemic shock or severe hypotension that requires pressors or surgery
 - Clinically overt or apparent bleeding associated with decrease in hemoglobin >5 g/dL
 - Bleeding requiring transfusion of ≥4 U whole blood or PRBCs
- **Other Major Bleeding** includes:
 - Bleed causing clinically significant disability (e.g., intraocular bleed with permanent vision loss)

- Clinically overt or apparent bleeding associated with decrease in hemoglobin >3 g/dL, but < 5 g/dL
 - Bleeding requiring transfusion of ≥ 2 , but < 4 U whole blood or PRBCs
- **Minor Bleeding** includes any bleeding requiring medical intervention but not meeting the criteria for major bleeding

Working Study Definitions:

- **Migraine Headache Day:** any study day in which headache symptoms occur. If a single headache lasts from the end of a calendar day into the beginning of the next, it would be considered a single headache day provided the event lasted less than 24 hours. If headache symptoms last more than 24 hours, it would be considered 2 Headache Days; more than 48 hours would be considered to be three days, etc. Aura alone ("Acephalic migraine") will not be considered a headache. The subject must experience headache pain.
- **"Responder" to Therapy:** $\geq 50\%$ reduction in the average number of monthly headache days during the month of therapy compared with participant's own baseline.
- **"Non-responder" to Therapy:** $< 50\%$ reduction in the number of monthly headache days during the month of therapy compared with participant's own baseline.
- **Platelet Inhibition:** This is a functional definition based on Platelet Reactivity. PRU Test Result (VerifyNow PRU Test, Accumetrics Inc. San Diego CA) of < 140 , while on therapy, will be considered a "positive" inhibitory effect of the medication. PRU results of $141 - 160$ will be considered a borderline response. PRU results > 161 will be considered a negative response.

Primary Study Endpoints:

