- Primary Efficacy Endpoint: A subject will be considered to have achieved the primary efficacy endpoint (a "Responder") if she/he has $\geq 50\%$ reduction in the number of monthly headache days during the month of therapy compared with participant's own baseline. If there is $< 50\%$ reduction in the number of migraine days, she/he will be considered a Non-Responder.
- Primary Safety Endpoint: Major bleeding episode (as defined above) or other life-threatening adverse event (see below), while taking the Brilinta/ticagrelor.

Secondary Study Endpoints:

- Secondary Efficacy Endpoints will be assessed as follows:
 - Absolute reduction in headache days as a continuous response variable.
 - Absolute reduction in headache intensity as a continuous response variable.

- Quantitative comparison of the number of monthly uses of rescue medications in the roll-in versus the treatment phase
- Comparison of time to headache resolution after rescue medications. If < 2 hours to resolution, will be considered a “successful” intervention. Will compare the percentage of successful interventions in the baseline and treatment phases.
- Secondary Safety endpoints: Non-life threatening adverse events to Brilinta/ticagrelor, including:
 - Minor bleeding
 - Allergic reactions
 - Shortness of Breath
 - Rash
 - Extreme fatigue
 - Any other symptom requiring the participant to withdraw from the study prior to completion of the one month medication administration

Subject Recruitment, Eligibility and Screening:

Study subjects will be recruited from hospital-based cardiology and headache clinic at Columbia University Medical Center, and through the private offices of the study physicians.

Preliminary Inclusion Criteria:

- Subject age 18 – 65 years
- Symptoms meet International Headache Society Criteria for Episodic Migraine or Chronic Migraine
- At least one year history of Episodic or Chronic migraine headache symptoms
- At least 6 headache days per month
- Subject agrees to use two forms of birth control or abstinence throughout duration of the study
- Subject able to complete online daily headache log
- Right to left shunt >grade 1 as determined by Transcranial Doppler evaluation

Preliminary Exclusion Criteria:

- Inability to understand the study or history of non-compliance with medical advice
- Currently taking a P2Y12 inhibitor
- Known hypersensitivity to Brilinta/ticagrelor
- History of stroke/transient ischemic attack (TIA) in the previous 6 months

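### The LOCF rule can count a subject who stops ticagrelor for an adverse event after two weeks as a Responder, and the plan's two statements of that rule differ on whether the logged days must be on drug

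*Combined protocol and SAP*

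**What the plan says.** Under Primary Study Endpoints, a Responder has at least a 50% "reduction in the number of monthly headache days during the month of therapy compared with participant's own baseline". Working Study Definitions gives the same threshold but refers to a "reduction in the average number of monthly headache days during the month of therapy". Both define response by headache days alone; neither says how stopping the drug affects the label.

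Partial data are handled in two places:

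- **Outcomes Assessment/Statistical Analysis, item 1.** The rule covers "Any participant who completes her/his daily headache logs for at least two weeks, but not the full month of the study period". Such a subject is "classified according to her/his current response status (LOCF), regardless of whether or not he/she completed the required therapy".
- **Withdrawal of Subjects.** The rule is repeated with a cross-reference to the Outcomes Assessment section, but covers a subject who "completes the daily headache logs for at least two weeks while on treatment".

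Withdrawal of Subjects adds two rules on data. After withdrawal for medical reasons, "all efficacy data collected to date will be maintained, but no further data will be collected". After consent is withdrawn for reasons other than an adverse event, "efficacy data already collected will no longer be eligible for review".

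The Outcomes Assessment section says that the observed response rate will feed the sample size of the later randomized trial. It also says that the results are descriptive and that drop-out from side effects will be assessed. Secondary Study Endpoints lists symptom-driven withdrawal as a safety outcome.

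**The concern.** The endpoint is a month's response, but a subject may be labelled on half a month. Someone withdrawn on day 15 for an adverse event, with headache days halved so far, has that status fixed because nothing more is collected. The responder count then does not separate this subject from one who completed the month.

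At stake is a planning figure. If the next trial is sized on a rate that includes people who could not stay on the drug, and that trial counts such people as non-responders, it will be too small. Intolerance is foreseeable: Dose Rationale and Risk/Benefits cites dyspnea in 14% of ticagrelor patients in the earlier coronary trial. The plan names no efficacy analysis set, no sensitivity analysis and no classification for subjects with less than two weeks of logs.

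The difference in wording adds a second problem: the same data can give two responder counts.

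**Working it through.** The documents give no expected response rate, drop-out rate, error rate or power, so there is no figure of the plan's own to reproduce here. Assumptions are marked.

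**1. Who is classified.** Set the two wordings against two subjects.

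| Subject | Analysis section | Withdrawal section |
|---|---|---|
| On drug and logging to day 15, then stopped for an adverse event | Classified by current status | Classified by current status |
| Stops drug on day 5, is not withdrawn, logs to day 14 only | Classified, mostly on off-drug days (9 of 14) | Not covered |

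The first row shows that the Responder label does not depend on the mismatch. The second row shows what the mismatch changes.

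**2. Size per subject.** Inputs: 40 treated, 20 per cohort. Moving one subject between categories shifts the rate by 1/40 = 2.5 points overall, or 1/20 = 5 points in a cohort. Assume 28/40 Responders under LOCF; 70% is used only as an anchor, from the clopidogrel experience in Study Purpose and Rationale. Let k be the assumed number of those 28 who stopped early for an adverse event or lack of effect. The rate is (28 − k)/40, with exact 95% intervals:

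- k = 0: 70.0% (53.5 to 83.4)
- k = 1: 67.5% (50.9 to 81.4)
- k = 2: 65.0% (48.3 to 79.4)
- k = 4: 60.0% (43.3 to 75.1)

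**3. Effect on the next trial.** Two proportions, pooled variance, two-sided 5%, 80% power:

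n per arm = [1.960·√(2p̄(1−p̄)) + 0.842·√(p₁(1−p₁) + p₂(1−p₂))]² / (p₁−p₂)²

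The control rates are assumptions. The planned trial is a cross-over, so these parallel-arm sizes show sensitivity only.

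| Control rate | 70% | 65% (k = 2) | 60% (k = 4) |
|---|---|---|---|
| 20% | 15 | 18 | 23 |
| 30% | 24 | 31 | 42 |
| 40% | 42 | 62 | 97 |

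From a lower assumed start, 20/40 (50%) against 18/40 (45%) gives 39 against 54 per arm at 20% control, and 93 against 163 at 30%.

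**4. Effect of the shorter window.** Model (assumption): independent days; 28-day baseline with daily probability 9/28 or 18/28, conditioned on at least 6 headache days; Responder if the count, scaled by 28/window, is at most half of baseline. Probability of a Responder label on 14 against 28 days:

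| True reduction | 9 days/month | 18 days/month |
|---|---|---|
| 0% | 13.3% v 6.4% | 1.3% v 0.1% |
| 30% | 35.5% v 29.6% | 20.0% v 12.6% |
| 50% | 57.8% v 58.9% | 53.8% v 54.3% |
| 60% | 70.0% v 74.7% | 72.7% v 78.4% |
| 70% | 81.7% v 88.0% | 87.9% v 93.7% |

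The shorter window raises the rate below about a 50% true reduction and lowers it above. If 4 of 40 subjects were classified at day 14, the overall shift at a 30% reduction would be 4/40 × (35.5 − 29.6) = 0.6 points or 4/40 × (20.0 − 12.6) = 0.7 points.

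**5. Scaling.** If a raw 14-day count were set against the 28-day baseline, the same model labels an unchanged subject a Responder 58.7% of the time at 9 days/month and 54.1% at 18. The plan does not rule this out.

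**The case against.** **Response and tolerability are separate questions.** The pilot asks whether P2Y12 inhibition relieves headache. Its definition of response uses headache days only, and side-effect drop-out is assessed separately. Calling an intolerant subject a failure is a choice of estimand that the protocol does not make. This stands. It is why the LOCF rate should still be shown, and why the argument rests on the rate's use for planning. Separate drop-out reporting does not show how many Responders were early stoppers.

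**The number of such subjects is invented.** This also stands. A reader might infer that the reported rate will contain treatment failures; the documents support only that it can. A shift of a few points is also well inside the intervals in step 2.

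**The mismatch is a drafting slip.** This is likely: the withdrawal section refers back to the analysis section, which merely lacks the on-treatment phrase. A reader might see two contradictory rules, but the text shows an omission. It also affects few people. Someone withdrawn for an adverse event on day 5 would not go on logging, because collection stops. It needs a subject who stops the drug without being withdrawn.

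**LOCF does not reach every early stopper.** A reader might take the rule to apply whatever the reason for stopping. It does not: efficacy data are set aside when consent is withdrawn for reasons unrelated to an adverse event. That removes some subjects from LOCF, and may remove those who leave for lack of benefit.

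**A shorter window need not inflate the rate.** Step 4 bears this out. If most subjects truly improve by more than half, as the clopidogrel series (13 of 15) might suggest, two-week classification lowers the rate.

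**Scaling may be implied.** Working Study Definitions speaks of an average monthly number, which can be read as a rate. The primary endpoint does not use that word, and the LOCF rule gives no method.

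**Conclusion.** The concern holds in limited form. Under either wording, a subject who stops for an adverse event after two weeks on drug, with at least a 50% reduction so far, can be counted as a Responder. The size is 2.5 points overall or 5 points in a cohort for each such subject, and the number of them is unknown. With two such subjects and a 70% starting rate, the illustrative next-trial size moves from 24 to 31 per arm at an assumed 30% control rate.

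The trial's own conclusions are descriptive and carry no error rate, so the damage is confined to the planning figure. The documents do not support a claim that the rate is certainly inflated, or that the two-week window by itself biases it upward. The on-treatment mismatch and the missing scaling rule are real gaps whatever the number of early stoppers. If raw counts were used, the scaling gap would be the larger error for each subject affected. The rules should be settled before the response data are examined.

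**What to change.** 1. Use one wording of the partial-data rule in the analysis plan and in Withdrawal of Subjects, counting on-drug days only.
2. State that a partial count is scaled to 28 days before comparison with the 28-day baseline: headache days × 28 / on-drug days logged.
3. Report the response rate over all treated subjects, overall and by cohort, counting those who stop study drug before day 28 for an adverse event or lack of effect as Non-responders. Use this rate to size the next trial. Show the LOCF rate beside it, with the number of early stoppers.
4. Reconcile item 3 with the rule that sets aside efficacy data after consent withdrawal for reasons other than an adverse event. One way is to count such treated subjects as Non-responders by disposition, without using their logs.

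This changes analysis and reporting only; no visit or treatment is affected. It costs wording edits in two sections, one extra tabulation and a reported rate that may be slightly lower.
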